### 8.2. Secondary Immunogenicity Analyses

#### 8.2.1. Maternal humoral immunity

Summaries and analysis of maternal humoral immunogenicity data will be presented by treatment group at one month after receipt of BOOSTRIX or Td, time of delivery, and 6 months after delivery. Serum IgG antibody concentrations to PT, FHA, PRN, tetanus and diphtheria will be summarized. Analysis will include GMCs along with corresponding 95% confidence intervals. The GMC between treatment groups will be compared using a t-test on log-transformed ELISA titers ([Table 25](#) and [Table 26](#)).

RCD curves for maternal subjects will be presented for serum IgG antibody concentrations to PT, FHA, PRN, tetanus and diphtheria. Plots will be generated with three panels (One Month After Vaccination, At Delivery, and 6 Months After Delivery), and separate curves within each panel for each treatment group, as shown in [Figure 27](#), [Figure 28](#), [Figure 29](#), [Figure 30](#), [Figure 31](#), [Figure 32](#), [Figure 33](#), [Figure 34](#), [Figure 35](#), and [Figure 36](#).

Log-transformed serum IgG antibody concentrations to PT, FHA, PRN, tetanus and diphtheria for maternal subjects will be plotted over time by treatment group along with the geometric mean at each time point ([Figure 81](#), [Figure 82](#), [Figure 83](#), [Figure 84](#), [Figure 85](#), [Figure 86](#), [Figure 87](#), [Figure 88](#), [Figure 89](#), and [Figure 90](#)). The GMCs and 95% confidence intervals of log-transformed serum IgG antibodies to each antigen will be plotted over time by treatment group in [Figure 135](#), [Figure 136](#), [Figure 137](#), [Figure 138](#), [Figure 139](#), [Figure 140](#), [Figure 141](#), [Figure 142](#), [Figure 143](#), and [Figure 144](#).

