3.1.2. Secondary

Immunogenicity:

- To assess the antibody response to BOOSTRIX vaccine antigens in pregnant women one month after receipt of BOOSTRIX, at the time of delivery, and at 6 months after delivery.
- To compare the antibody levels of BOOSTRIX vaccine antigens at birth (cord blood) and 6 weeks of age (before receiving any infant doses of Diphtheria, Tetanus, and whole-cell Pertussis (DTwP)) in infants whose mothers received BOOSTRIX or Td during pregnancy.
- To assess placental antibody transfer by determining the ratio of maternal and infant BOOSTRIX -specific antibody responses at delivery.
- To assess interference with infant antibody responses to DTwP either prior to the second dose of the primary DTwP series, at approximately 10 weeks of age (in ½ of subjects), or approximately one month after the third dose of the primary DTwP series, at approximately 18 weeks of age (in ½ of subjects), and at 6 months of age (all subjects).

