6. STUDY INTERVENTION/INVESTIGATIONAL PRODUCT

6.1. Study Product Description

BOOSTRIX

BOOSTRIX (Tetanus Toxoid, Reduced Diphtheria Toxoid, and Acellular Pertussis Vaccine, Adsorbed) is a noninfectious, sterile, vaccine for intramuscular administration. It contains tetanus toxoid, diphtheria toxoid, and pertussis antigens (inactivated PT, formaldehyde-treated FHA, and PRN). The antigens are the same as those in INFANRIX, but BOOSTRIX is formulated with reduced quantities of these antigens.

Tetanus toxin is produced by growing *Clostridium tetani* in a modified Latham medium derived from bovine casein. The diphtheria toxin is produced by growing *Corynebacterium diphtheriae* in Fenton medium containing a bovine extract. The bovine materials used in these extracts are sourced from countries which the United States Department of Agriculture (USDA) has determined neither have nor are at risk of bovine spongiform encephalopathy (BSE). Both toxins are detoxified with formaldehyde, concentrated by ultrafiltration, and purified by precipitation, dialysis, and sterile filtration.

The acellular pertussis antigens (PT, FHA, and PRN) are isolated from *Bordetella pertussis* culture grown in modified Stainer-Scholte liquid medium. PT and FHA are isolated from the fermentation broth; PRN is extracted from the cells by heat treatment and flocculation. The antigens are purified in successive chromatographic and precipitation steps. PT is detoxified using glutaraldehyde and formaldehyde. FHA and PRN are treated with formaldehyde.

Tetanus and diphtheria toxoid potency is determined by measuring the amount of neutralizing antitoxin in previously immunized guinea pigs. The potency of the acellular pertussis components (inactivated PT, formaldehyde-treated FHA, and PRN) is determined by ELISA on sera from previously immunized mice.

BOOSTRIX is manufactured by GSK and is approved for use in the US in persons 10 years and old and by the WHO for persons 4 years and older. In Mali, the vaccine is not approved by the national drug authority.

Tetanus and Diphtheria Toxoids Adsorbed (Td) Control Vaccine

The Td control vaccine is prequalified by WHO and will be provided by the Ministry of Health in Mali, as per standard of care. It is indicated for the active immunization of adults and children 7 years of age and older against diphtheria and tetanus. Vaccine manufacturer details will be provided in the protocol-specific Manual of Procedures (MOP).

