6.1.2. Formulation, Packaging, and Labeling

BOOSTRIX

Formulation

Each 0.5-mL dose of vaccine is formulated to contain 5 Lf of tetanus toxoid, 2.5 Lf of diphtheria toxoid, 8 mcg of inactivated PT, 8 mcg of FHA, and 2.5 mcg of PRN (69 kiloDalton outer membrane protein). Each 0.5-mL dose contains aluminum hydroxide as adjuvant (not more than 0.39 mg aluminum by assay), 4.4 mg of sodium chloride, \leq 100 mcg of residual formaldehyde, and \leq 100 mcg of polysorbate 80 (Tween 80).

Storage

The vaccine must be stored at 2°C to 8°C (35°F to 46°F). Do not freeze.

Packaging and Labeling

The vaccine is supplied as 0.5 mL single-dose prefilled syringes. The tip caps of the prefilled syringes contain natural rubber latex; the plungers are not made with natural rubber latex. The study product will be labeled according to manufacturer specifications and include the statement “Caution: New Drug – Limited by Federal Law to Investigational Use.”

Td Control Vaccine

Formulation

The vaccine contains purified tetanus and diphtheria toxoids, with a reduced dose of the diphtheria component. One dose of 0.5 mL has a potency of less than 30 IU of diphtheria toxoid, and not less than 40 IU of tetanus toxoid. The toxoids are adsorbed onto at least 1.5 mg aluminum phosphate. Thimerosal 0.1 mg/ml is used as a preservative.

Storage

The vaccine should be protected from light and must be stored at 2°C to 8°C (36°F to 46°F). Do not freeze.

Packaging

The vaccine is supplied as 10-dose vials of 5 mL.

Multi-dose vials of Td control vaccine from which one or more doses of vaccine have been removed during an immunization session may be used in subsequent immunization sessions for up to a maximum of 4 weeks, provided that all of the following conditions are met:

- The expiry date has not passed;
- The vaccines are stored under appropriate cold chain conditions;
- The vaccine vial septum has not been submerged in water;
- Aseptic technique has been used to withdraw all doses;
- The vaccine vial monitor, if attached, has not reached the discard point.

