7.3. Enrollment/Baseline

Enrollment and Vaccination Visit, Day 1: Clinic Visit, Pregnant Women (Visit 01 or V01)

- Reconfirm subject's willingness to participate prior to performing any study procedures, including administration of the study vaccination.
- Obtain informed consent (if screening and enrollment visits have been combined).
- Review eligibility criteria with subjects prior to the study vaccination to ensure eligibility.
- Complete medical history and any updates obtained by interview and/or review of medical charts of subjects since the screening visit will be reviewed with subjects prior to the study vaccination to ensure eligibility.
- All concomitant medications and vaccinations will be reviewed with subjects prior to the study vaccination for accuracy and completeness. Any new concomitant medications/vaccinations taken since the screening visit will be reviewed with subjects and used in the assessment for eligibility, prior to the study vaccination. Medications reported in the eCRF are limited to those taken within 30 days prior to the study vaccination. Subjects will be reminded they should not plan to receive any live or inactivated vaccine within 30 or 14 days, respectively, after study vaccination.
- Vital signs, namely oral temperature, pulse, and blood pressure, will be obtained prior to the study vaccination. Vital signs assessed on Day 1 prior to the study vaccination will be considered as baseline. Subjects will be asked not to eat or drink anything hot or cold, or smoke within 10 minutes prior to taking an oral temperature.

- Height and weight will be obtained, if not done on screening visit.
- A targeted physical examination may be performed prior to the study vaccination by a study clinician licensed to make medical diagnoses and listed on the Form FDA 1572 as the site principal investigator or sub-investigator, if indicated based on review of complete medical history and any updates obtained by interview of subjects or medical chart review since the screening visit. For pregnant women, an examination performed by her own obstetrical clinician may also provide data when a targeted exam is called for.
- Approximately 30 mL of venous blood will be collected immediately prior to the study vaccination for baseline serology and cytokine assays.
- Subjects will be enrolled in Advantage eClinical and assigned to treatment arm (BOOSTRIX or Td) and post-partum study schedule.

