##### **3.1.2. Secondary**

###### **Immunogenicity:**

- To assess the antibody response to BOOSTRIX vaccine antigens in pregnant women one month after receipt of BOOSTRIX, at the time of delivery, and at 6 months after delivery.
- To compare the antibody levels of BOOSTRIX vaccine antigens at birth (cord blood) and 6 weeks of age (before receiving any infant doses of Diphtheria, Tetanus, and whole-cell Pertussis (DTwP)) in infants whose mothers received BOOSTRIX or Td during pregnancy.
- To assess placental antibody transfer by determining the ratio of maternal and infant BOOSTRIX - specific antibody responses at delivery.
- To assess interference with infant antibody responses to DTwP either prior to the second dose of the primary DTwP series, at approximately 10 weeks of age (in ½ of subjects), or approximately one month after the third dose of the primary DTwP series, at approximately 18 weeks of age (in ½ of subjects), and at 6 months of age (all subjects).

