#### 3.2.2. Secondary

##### Immunogenicity:

- Maternal humoral immunity: GMC of serum IgG antibodies to Tdap vaccine antigens (PT, FHA (Filamentous Hemagglutinin), PRN (Pertactin), tetanus, diphtheria) as measured by ELISA in pregnant women one month after receipt of BOOSTRIX or Td, at the time of delivery, and 6 months after delivery.
- Infant humoral immunity: GMC of serum IgG antibodies to Tdap vaccine antigens (PT, FHA, PRN, tetanus, diphtheria) as measured by ELISA at birth and prior to receipt of first DTwP (approximately 6 weeks of age) among infants born to women vaccinated with BOOSTRIX compared to Td.

- Placental antibody transfer: The geometric mean ratio (GMR) of maternal and infant-specific Tdap-specific antibodies (PT, FHA, PRN, tetanus, diphtheria) as measured by ELISA at delivery after intrapartum receipt of BOOSTRIX versus Td.
- Interference with infant responses among infants whose mothers received intrapartum BOOSTRIX compared to Td: GMC of antibodies to DTwP vaccine antigens (PT, FHA, PRN, Fimbriae 2 (FIM2), Fimbriae 3 (FIM3), tetanus, diphtheria) as measured by ELISA one month after the first dose of DTwP (~10 weeks of age, ½ of infants), one month after the third dose of DTwP vaccine (~18 weeks of age, ½ of infants), and at 6 months of age.

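### The maternal antibody tables omit the Day 1 result, so they do not show whether either vaccine raised tetanus or diphtheria antibody

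*SAP*

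**What the plan says.** The secondary objective in Protocol 3.1.2, repeated in SAP 3.1.2, begins "To assess the antibody response to BOOSTRIX vaccine antigens in pregnant women one month after receipt of BOOSTRIX" and goes on to delivery and 6 months postpartum. It is worded as a response and is not limited to the pertussis antigens. The matching endpoint in SAP 3.2.2 is a GMC "as measured by ELISA in pregnant women one month after receipt of BOOSTRIX or Td, at the time of delivery, and 6 months after delivery". It covers five antigens: tetanus and diphtheria, and the pertussis components PT, FHA and PRN.

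The analysis keeps to those three times. SAP 4.5.2 names only those draws for maternal humoral immunity, and SAP 8.2.1 has the summaries "presented by treatment group at one month after receipt of BOOSTRIX or Td, time of delivery, and 6 months after delivery". The Table 25 shell has three rows per antigen, and Table 26 copies its format. The reverse cumulative distribution plots (Figures 27–36) have three panels. The only comparison is a t-test between arms on log titers, with no baseline term.

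Day 1 serum is nevertheless collected. Protocol 7.3 states: "Approximately 30 mL of venous blood will be collected immediately prior to the study vaccination for baseline serology and cytokine assays". SAP 6.3.2 removes women with no baseline result from the maternal per-protocol population, and Table 11 counts them.

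On content, Protocol 6.1 lists tetanus toxoid, diphtheria toxoid, PT, FHA and PRN for BOOSTRIX. Of the Td control, Protocol 6.1.2 says: "The vaccine contains purified tetanus and diphtheria toxoids, with a reduced dose of the diphtheria component".

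**The concern.** For PT, FHA and PRN the Td arm receives none of the antigen, so the randomised contrast estimates what BOOSTRIX did. For tetanus and diphtheria both arms are vaccinated. A high one-month GMC may be antibody that the women already had, which is plausible because Protocol 2.1.8 describes tetanus-containing vaccine as recommended at the first pregnancy contact in Mali. Equal GMCs in the two arms may mean two good responses or none. A ratio away from 1 would show that the vaccines act differently, but not how far either moved the level.

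At stake is what the report can say about response for two of the five BOOSTRIX antigens. The plan already treats the exploratory maternal cytokines differently: Table 33 gives them a pre-vaccination row and a change row. The secondary antibody endpoint gets neither.

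**Working it through.** **Inputs**
- Arm sizes: 133 and 67 (Protocol 11.2.3).
- Loss: 15% (Protocol 5.3.5 and 11.2.2), giving 133 × 0.85 = 113 and 67 × 0.85 = 57. Section 11.2.2 ties this rate to the primary immunogenicity outcome; applying it to the maternal set is my assumption.
- Maternal log-SD at delivery (Protocol Table 10, SAP Table 4): PT 0.90, FHA 0.73, PRN 1.45. There is no tetanus or diphtheria row, and no within-woman correlation is given.

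**1. The plan's nearest own figure.** The point disputes no stated number, but the interval formula can be checked on the same endpoint: GMC × exp(± t(0.975, n−1) × SD/√n). For PT with n = 133:

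51 × exp(± 1.978 × 0.90/√133) = 51 × exp(± 0.154) = 43.7 to 59.5

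Table 10 states 43.7 to 59.5. FHA gives 163.1 to 209.5 (stated 163.1 to 209.3) and PRN 143.9 to 236.6 (stated 143.8 to 236.7). The plan's figures are reproduced apart from rounding, so the same formula is used in step 3.

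**2. What the planned rows can tell apart.** Suppose the one-month tetanus GMC is 1.0 in both arms (arbitrary units, illustrative values). Fold rise = one-month GMC / Day 1 GMC.

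| Day 1 GMC, both arms | One-month GMC, both arms | BOOSTRIX/Td ratio | Fold rise |
|---|---|---|---|
| 0.2 | 1.0 | 1.0 | 5 |
| 0.5 | 1.0 | 1.0 | 2 |
| 1.0 | 1.0 | 1.0 | 1 |

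Tables 25–26 print the second column and the arm comparison. These are identical in all three cases, so the planned summaries cannot separate a response from existing antibody.

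**3. Whether the missing quantity can be estimated.** With equal SD s at both visits and within-woman correlation ρ, the paired log difference has SD = s√(2(1−ρ)). The 95% CI for the geometric mean fold rise is the estimate multiplied and divided by exp(t × SD/√n). At s = 0.90 and ρ = 0.5 the SD is 0.90 × √1 = 0.90, and the factors are:
- BOOSTRIX: 1.17 (n = 133) or 1.18 (n = 113)
- Td: 1.25 (n = 67) or 1.27 (n = 57)

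Over s from 0.73 to 1.45 and ρ from 0 to 0.7 the ranges are:
- BOOSTRIX: 1.10 to 1.42 (n = 133) or 1.11 to 1.47 (n = 113)
- Td: 1.15 to 1.65 (n = 67) or 1.16 to 1.72 (n = 57)

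Even at the wide end, a 2-fold rise in the smallest group would have a lower limit of 2/1.72 = 1.16.

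**4. Which between-arm comparison to keep.** Relative to the variance of the post-vaccination log titer, an unadjusted change score has variance 2(1−ρ) and a baseline-adjusted comparison has 1−ρ². At ρ = 0.3 these are 1.40 and 0.91; at ρ = 0.5, 1.00 and 0.75; at ρ = 0.7, 0.60 and 0.51. Below ρ = 0.5 a ratio of fold rises is less precise than the GMC ratio already planned. The adjusted comparison is not worse at any of these values.

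**The case against.** The strongest reply is that the plan delivers what it defines. The endpoint attached to the objective is the post-vaccination GMC at three named times, and Tables 25–26 give it for all five antigens with intervals and an arm comparison. That is correct. It does not remove the point, because for tetanus and diphtheria this endpoint measures a level while the objective names a response.

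A second reply is that randomisation balances baseline in expectation, so BOOSTRIX versus Td is a fair comparison without Day 1. This also stands. A reader might infer that the trial cannot inform the substitution of Tdap for Td raised in Protocol 2.2. The documents do not support that: substitution asks how the two vaccines compare, and the planned contrast estimates it.

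A third reply is that Listing 8 prints individual titers by planned time point with no stated restriction to visits after vaccination. Day 1 values may well appear there. A listing, however, carries no estimate or interval.

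Two further inferences should be resisted. Figures 81–90 and 135–144 are described only as plots over time. SAP 8.2.1 names no time points for them and the images are not available in the text reviewed, so it cannot be said that they omit Day 1. And the general reporting sentence in Protocol 11.4.3, which promises results at every time point, does not name Day 1, so it is not a clear breach.

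**Conclusion.** The point holds as an omission from the planned summaries. For two of the five maternal antigens, at all three times, SAP 4.5.2, SAP 8.2.1, Tables 25–26 and Figures 27–36 give no within-arm rise, and the planned tables do not answer the response objective for those antigens.

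A reader might go further and say that the objective cannot be answered at all. The documents do not support this: the serum is drawn before vaccination for serology, and baseline results are expected in the per-protocol set. For PT, FHA and PRN nothing essential is missing, since the arm contrast estimates the vaccine effect.

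The conclusion on what the tables can show rests only on vaccine content and the listed time points. The precision figures rest on assumed SDs and correlations. Reading a one-month fold rise as vaccine response also assumes little other change over that month, because a before-and-after change is not a randomised contrast. The trial is an estimation study and this endpoint is secondary, so this is a worthwhile, inexpensive improvement and not a threat to the primary analysis.

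**What to change.** - Amend SAP 4.5.2 and 8.2.1 to include the Day 1 maternal serum result.
- Add a Day 1 GMC row to Tables 25–26 and a Day 1 panel to Figures 27–36. Confirm that Figures 81–90 and 135–144 include Day 1.
- For each arm and antigen, report the paired geometric mean fold rise from Day 1 with its 95% CI, computed on the log scale. Base any statement about tetanus or diphtheria response on it.
- Keep the planned post-vaccination GMC comparison between arms. If a comparison that uses baseline is wanted, model the log titer with arm and log Day 1 titer, not an unadjusted ratio of fold rises.

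The cost is some SAP text, revised shells and a small amount of extra analysis. No visit or blood draw is added. Women without a Day 1 result drop out of the fold-rise rows, so the number contributing should be printed.

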### 8.2.2. Infant humoral immunity

Summaries and analysis of infant humoral immunogenicity data will be presented by treatment group at birth and prior to receipt of first DTwP. Serum IgG antibody concentrations to PT, FHA, PRN, tetanus, and diphtheria will be summarized. Analysis will include GMCs along with corresponding 95% confidence intervals. The GMC between treatment groups will be compared using a t-test on log-transformed ELISA titers (Table 23 and Table 24).

RCD curves for infants will be presented for serum IgG antibody concentrations to PT, FHA, PRN, tetanus and diphtheria. Plots will be generated with two panels (Birth and Prior to Receipt of First Dose of DTwP), and separate curves within each panel for each treatment group, as shown in Figure 3, Figure 4, Figure 5, Figure 6, Figure 7, Figure 8, Figure 9, Figure 10, Figure 11, and Figure 12.

Log-transformed serum IgG antibody concentrations to PT, FHA, PRN, tetanus and diphtheria for infants will be plotted over time by treatment group along with the geometric mean at each time point (Figure 57, Figure 58, Figure 59, Figure 60, Figure 61, Figure 62, Figure 63, Figure 64, Figure 65, and Figure 66). The GMCs and 95% confidence intervals of log-transformed serum IgG antibodies to each antigen will be plotted over time by treatment group in Figure 111, Figure 112, Figure 113, Figure 114, Figure 115, Figure 116, Figure 117, Figure 118, Figure 119, and Figure 120.

### 8.2.3. Placental antibody transfer

Summaries and analysis of immunogenicity data will be presented by treatment group for placental antibody transfer where data is available for both mother and child at delivery/birth. Serum IgG antibody concentrations to PT, FHA, PRN, tetanus and diphtheria will be summarized. Analysis will include Geometric Mean Ratios (GMRs) along with corresponding 95% confidence intervals (Table 27 and Table 28).

### 8.2.4. Inference with infant responses among infants whose mothers received intrapartum BOOSTRIX compared to Td

Summaries and analysis of immunogenicity data will be presented by treatment group at one month after receipt of first DTwP, one month after receipt of third DTwP, and at 6 months of age. DTwP antibody concentrations to PT, FHA, PRN, FIM2, FIM3, tetanus and diphtheria, will be summarized. Analysis will include GMCs along with corresponding 95% confidence intervals. The GMC between treatment groups will be compared using a t-test on log-transformed ELISA titers (Table 23 and Table 24).

RCD curves for infants will be presented for DTwP antibody concentrations to PT, FHA, PRN, FIM2, FIM3, tetanus and diphtheria. Plots will be generated with three panels (One Month After Receipt of First Dose of DTwP, One Month After Receipt of Last Dose of DTwP, and 6 Months of Age), and separate curves within each panel for each treatment group, as shown in Figure 13, Figure 14, Figure 15, Figure 16, Figure 17, Figure 18, Figure 19, Figure 20, Figure 21, Figure 22, Figure 23, Figure 24, Figure 25, and Figure 26.

Log-transformed DTwP antibody concentrations for infants to PT, FHA, PRN, FIM2, FIM3, tetanus and diphtheria will be plotted over time by treatment group along with the geometric mean at each time point (Figure 67, Figure 68, Figure 69, Figure 70, Figure 71, Figure 72, Figure 73, Figure 74, Figure 75, Figure 76, Figure 77, Figure 78, Figure 79, and Figure 80). The GMCs and 95% confidence intervals of log-transformed serum IgG antibodies to each antigen will be plotted over time by treatment group in Figure 121, Figure 122, Figure 123, Figure 124, Figure 125, Figure 126, Figure 127, Figure 128, Figure 129, Figure 130, Figure 131, Figure 132, Figure 133, and Figure 134.

